7.2 Collection and Derivation of Primary and Secondary Efficacy Assessments

For analysis purposes, four weeks (28 days) will be considered as one month. On a daily basis during the 28-day baseline period and throughout the double-blind treatment period, patients are to record into an eDiary information on the daily total duration of headache, headache specific characteristics and symptoms, the worst pain severity, and use of any acute headache pain medication. Patients will be able to report headache data, including absence of headache, for the day of the diary report and for the day immediately prior to the day of the diary report, as long as information reported is for a time subsequent to the patient's most recent report. This is defined as a one-day "missing-recall" window.

Following randomization on Day 1, there are 4 visits at 2-week intervals, followed by 2 visits at 4-week intervals; altogether encompassing a 12-week double-blind treatment phase of the study and a 4-week safety follow-up phase. In practice, there may or may not be exact 2-week or 4-week durations between two consecutive visits and the visits might not align with each 28-day period recorded in the eDiary (ie, weeks 1-4, 5-8 and 9-12, corresponding to days 1-28, 29-56 and 57-84). Therefore, for data analysis purposes, the number of migraine/probable migraine headache days during the first 28 days of the baseline phase, starting with the day of the screening visit, will serve as the "baseline", and change from baseline will be calculated for consecutive 28-day periods beginning with Day 1.

In order to be randomized, a patient should be in the baseline phase for at least 28 days and must report diary data for at least 20 days (including missing recall) during the 28-day baseline period. If less than 28 days of baseline data are reported, the number of headache days and other such counting variables for "baseline" will be prorated to standardize the count to a 28-day equivalent. Subsequent to treatment start, the number of headache days will be counted in successive and non-overlapping 4-week (ie, 28-day) windows. Headaches that continue into a subsequent 4-week period will be counted (with recorded severity and duration) as occurring in each period.

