4.1 Study Design Summary

This is a multi-center, randomized, double-blind, placebo-controlled, parallel group study conducted at approximately 75 sites in the United States. Approximately 810 participants will be randomized to one of six treatment arms (placebo, 10-mg once daily [QD], 30-mg QD, 30-mg twice daily [BID], 60-mg QD, and 60-mg BID) in a 2:1:2:1:2:1 ratio as follows:

- Placebo (n = 180)
- Atogepant 10-mg QD (n = 90)
- Atogepant 30-mg QD (n = 180)
- Atogepant 30-mg BID (n = 90)
- Atogepant 60-mg QD (n = 180)
- Atogepant 60-mg BID (n = 90)

To maintain the blind, investigational product will be administered orally BID for 12 weeks to all participants. Participants, therefore, will receive either placebo twice daily, a morning dose of atogepant with an evening dose of placebo, or atogepant twice daily.

Subject participation will begin with a 4-week Screening/Baseline Period. Participants who complete the 4-week Screening/Baseline Period and meet all entry criteria will be randomized to the double-blind treatment period of the study at Visit 2 (randomization visit). The double-blind treatment period will last 12 weeks, with a subsequent Safety Follow-up Period of 4 additional weeks. There will be 8 scheduled clinic visits: Visit 1 (Screening/Baseline), Visit 2 (Randomization), Visit 3 (Week 2), Visit 4 (Week 4), Visit 5 (Week 6), Visit 6 (Week 8), Visit 7/ET (Week 12), and Visit 8 (Safety Follow-up). For details, please see Table 4–2, Schedule of Visit and Procedures.

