5.1.1.1 Common Conventions

5.1.1.1.1 Analysis Populations

The analysis populations will consist of participants as defined below:

Population Definition		Study Treatment
Screened	All screened participants who sign informed consent	—
Intent-to-Treat (ITT)	All randomized participants	Randomized assignment
Modified Intent-to- Treat (mITT)	 All randomized participants who received ≥ 1 dose of study treatment, had an evaluable baseline period of diary data, and had ≥ 1 evaluable post-baseline 4-week (Weeks 1-4, 5-8, and 9-12) of diary data For baseline, evaluable is defined as having at least 20 days of diary data during the 4-week baseline period For each post-baseline 4-week treatment period, evaluable is defined as having at least 12 days of diary data for that particular period 	Randomized assignment
Safety	ty All participants who received ≥ 1 dose of study treatment Actual received	

Table 5–1Analysis Populations

¹ Participants will be summarized according to the study treatment received for majority of treatment period.

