#### 5.1.2 **Determination of Sample Size**

With this multiplicity strategy as described in Section 5.1.1.3.3, the assumptions and corresponding power assessments for the primary efficacy endpoint are shown in Table 5–25. The treatment differences are assumed based on results from other episodic migraine prevention studies. The placebo-adjusted reduction in monthly migraine days observed from other episodic migraine prevention studies ranged from 1.1 to 2 days [topiramate (Silberstein 2004 and Brandes 2004), telcagepant (Ho 2014), and CGRP monoclonal antibodies Ph2 studies (Dodick 2014; Dodick 2014; Sun 2016), and their Ph3 studies results reported from American Headache Society & American Academy of Neuroscience 2017]. Power is calculated via 10,000 simulations based on multiplicity adjustment as described in Figure 5-1 for the 5 doses and primary and secondary endpoints.

Table 5–25	Assumed Effect Size and Estimated Power for Primary Efficacy Endpoint				
	60 mg BID (n=90)	30 mg BID (n=90)	60 mg QD (n=180)	30 mg QD (n=180)	10 mg QD (n=90)
Assumed Treatment difference vs. placebo (placebo n = 180)	-1.6	-1.5	-1.5	-1.4	-1.2
Effect size (Common SD ¹ = 3.0)	0.53	0.5	0.5	0.47	0.4
Power	97.0%	91.4%	99.3%	98.1%	80.3%

¹ Common standard deviation is estimated based on blinded interim data assessments.

QD = once daily; BID = twice daily; SD = standard deviation.

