The 4-week *(monthly)* MPM headache days is defined as the total number of reported MPM headache days in the diary divided by the total number of days with diary records during each 4-week period and multiplied by 28. A minimum of 12 days' diary data during each *postbaseline* 4-week treatment period is required in order for the MPM headache migraine days to be evaluable for that particular period. If a subject does not have at least 12 days of diary data for any 4-week treatment period, the MPM headache days for that particular period will be considered as missing. MPM headache days will be derived for each participant at baseline and for each *postbaseline* 4-week treatment period (Weeks 1-4, 5-8, 9-12). The same method to derive MPM headache days will be used to derive headache days, *acute medication use days, and triptan use days*.

If a subject reports 'Yes' to the intake of allowed medication(s) to treat an acute migraine but does not list any of them in the diary, then the acute medication use days will not be counted in this situation.

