## 6.4.2 Primary Efficacy Analysis

The primary efficacy endpoint is the change from baseline in mean monthly MPM headache days across the 12-week treatment period. The endpoint will be analyzed using MMRM. The response variable is the change from baseline to each postbaseline month in monthly MPM headache days. The model will include baseline monthly MPM headache days as a covariate, treatment group and visit (month) as fixed factors, and treatment group-by-visit and baselineby-visit as interaction terms. The analysis will be performed based on evaluable postbaseline data using only the observed cases without imputation of missing values.

Restricted maximum likelihood method will be used. The within-patient correlation will be modeled using the unstructured covariance matrix. If the model does not converge, then the compound symmetry covariance structure will be used. The Kenward-Roger approximation will be used to estimate denominator degrees of freedom. Contrasts will be constructed to obtain the average treatment effects across the 12-week treatment period to compare each atogepant treatment group versus the placebo group. Each treatment effect and treatment comparisons will be estimated by the LS Means and their differences in LS Means, along with their SE and 95% confidence intervals, and the p-value corresponding to the betweentreatment group difference.

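### Are the stated powers too high because they use the randomised numbers, while the primary analysis uses only evaluable patients and months?

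*SAP*

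**What the plan says.** SAP 5.1.2 (Table 5-25) and Protocol 7.7 give the same five powers for the primary endpoint: 97.0% (60 mg BID), 91.4% (30 mg BID), 99.3% (60 mg QD), 98.1% (30 mg QD) and 80.3% (10 mg QD). The column headings show n = 90 or 180 and the row label reads "Assumed Treatment difference vs. placebo (placebo n = 180". These numbers sum to the planned enrolment in SAP 4.1: "Approximately 810 participants will be randomized to one of six treatment arms". On the SD, the SAP footnote says only: "Common standard deviation is estimated based on blinded interim data assessments".

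The analysis itself rests on fewer data. SAP 6.4.2 states: "The analysis will be performed based on evaluable postbaseline data using only the observed cases without imputation of missing values". In the mITT definition (SAP 5.1.1.1.1), for each post-baseline period, "evaluable is defined as having at least 12 days of diary data for that particular period". Below that threshold, under SAP 6.4.1, "the MPM headache days for that particular period will be considered as missing".

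Two features work the other way. Entry requires a well-kept baseline diary, since under Protocol 7.2 a patient "must report diary data for at least 20 days (including missing recall) during the 28-day baseline period". The analysis also adjusts for baseline: "The model will include baseline monthly MPM headache days as a covariate".

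**The concern.** A power figure should describe the analysis that will be run. Here the n in the table is everyone randomised, whereas the test uses patients with an evaluable baseline and at least one evaluable month, and only their evaluable months. Some loss is certain in a 12-week diary trial, and the SAP plans a missing-data sensitivity analysis because of it. If nothing was allowed for loss, every stated power would be somewhat too high.

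The dose with least room is 10 mg QD, stated at 80.3%, followed by 30 mg BID at 91.4%. Protocol 3.1 defends the smaller BID and 10 mg QD arms as adequately powered, so these figures support a statement in the protocol.

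**Working it through.** **Inputs from the documents.** Differences 1.6, 1.5, 1.5, 1.4 and 1.2 days; SD 3.0; placebo n = 180; active n = 90, 90, 180, 180 and 90; two-sided tests; alpha 0.025 for each 60 mg dose, then the graph of SAP 5.1.1.3.3. The documents give no dropout rate, no derivation of the SD and no assumed effects for the secondary endpoints.

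**Step 1: reproduce the stated powers.** The two 60 mg comparisons do not depend on recycled alpha. Power = Φ(δ / [σ√(1/n₁ + 1/n₂)] − z), with z = 2.241 for two-sided 0.025.

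- 60 mg BID: 1.6 / (3.0 × √(1/90 + 1/180)) = 1.6 / 0.3873 = 4.131; Φ(4.131 − 2.241) = 97.1% (96.9% with the noncentral t). Stated: 97.0%.
- 60 mg QD: 1.5 / (3.0 × √(2/180)) = 1.5 / 0.3162 = 4.743; Φ(4.743 − 2.241) = 99.4% (99.35% with the noncentral t). Stated: 99.3%.

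At 5% loss, 60 mg BID is Φ(4.131 × √0.95 − 2.241) = 96.3%. With 10,000 simulations the standard error is √(0.97 × 0.03 / 10,000) = 0.17 points, so 96.3% is about 4 standard errors from the stated value. At SD 3.0 the table therefore uses the full randomised n, or very nearly so (1% loss gives 96.9% and cannot be excluded).

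**Step 2: the cost of loss if 3.0 is exactly right.** The whole graph was simulated with n scaled by (1 − loss). The secondary endpoints were assumed to have 0.8 of the primary standardised effect and correlation 0.6. Figure 5-1 is not available, so the BID edges follow the SAP text.

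| Loss | 60 BID | 30 BID | 60 QD | 30 QD | 10 QD |
|---|---|---|---|---|---|
| Stated | 97.0 | 91.4 | 99.3 | 98.1 | 80.3 |
| 0% | 97.1 | 91.4 | 99.4 | 97.8 | 80.5 |
| 3% | 96.6 | 90.2 | 99.2 | 97.4 | 78.7 |
| 5% | 96.3 | 89.4 | 99.1 | 97.0 | 77.5 |
| 10% | 95.2 | 86.8 | 98.8 | 96.0 | 74.1 |

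The level for 10 mg QD depends heavily on the assumed secondary effects: at zero loss it runs from about 69% with no recycling to about 86% if every secondary succeeds. The drop at 5% loss depends on them much less, at 2.1 to 3.1 points.

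**Step 3: how large the loss might be.** Assume dropout spread evenly over 84 days. Under the 12-day rule, 12/84 = 14% of dropouts have no evaluable month, 28/84 = 33% have one, 33% have two and 16/84 = 19% keep all three. For the three-month mean under compound symmetry with an assumed monthly correlation of 0.4 to 0.8, 10% dropout costs 2.0 to 3.3% of the information and 20% costs 4.1 to 6.7%. The added noise of prorated short months is not modelled.

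**Step 4: what the SD of 3.0 may already contain.**

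- *Pooled blinded SD.* With allocation weights 2:1:1:2:2:1 over 9 (placebo, 60 BID, 30 BID, 60 QD, 30 QD, 10 QD), the assumed differences have mean 10.1/9 = 1.122 and mean square 14.67/9 = 1.630. The between-arm variance is 1.630 − 1.122² = 0.371. The within-arm SD is then √(9 − 0.371) = 2.94, which offsets a loss of 0.371/9 = 4.1%. With SD 2.94 and 5% loss the five powers, in the table's order, are 96.9, 91.1, 99.4, 97.7 and 79.9%, close to those stated.
- *Raw SD.* Baseline adjustment multiplies the variance by (1 − r²), where r is the correlation of change with baseline. It cancels 3, 5 or 10% loss at r = 0.17, 0.22 or 0.32.
- *Both, with r = 0.2 assumed.* 8.629 × 0.96 = 8.284, and 1 − 8.284/9 = 8.0%. That exceeds the loss in Step 3 even at 20% dropout.
- *SD from available months.* If the blinded SD was computed from each patient's available months, the variance due to missing months is already in 3.0. Only patients with no evaluable month would then be lost: 14% of 10% dropout, about 1.4%.

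**The case for a change.** The best argument for changing the plan is that a reader cannot tell which SD the 3.0 is, and so cannot tell whether the powers describe the planned analysis. The documents foresee loss: they list reasons for discontinuation, require withdrawal in some cases and plan a sensitivity analysis for data not missing at random. All five doses are to be tested for superiority in a pivotal trial. The 80.3% for 10 mg QD also needs recycled alpha, because at the 0.01 level in SAP 5.1.1.3.3 it is only about 69 to 70% at full n. A rerun and two table edits would cost little.

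The facts in this stand. The table uses the randomised n, the evaluable loss and the origin of the SD are unstated, and at a fixed SD any loss lowers power, most for 10 mg QD. The step to powers that are too high does not stand, because the likely loss and the possible offsets are of similar size. The arm sizes are printed in the table. SAP 5.1.2 says the simulation covers the five doses with primary and secondary endpoints, and 5.1.1.3.3 describes the recycling. A grid of powers at assumed loss rates would add scenarios, without settling which one applies.

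**Conclusion.** No change follows. This is an unstated planning assumption in a table that reproduces on its printed inputs (30 mg QD is the loosest fit, 97.8% against 98.1%). If 3.0 is the SD of the baseline-adjusted contrast, 5% information loss lowers 10 mg QD by about 2 to 3 points, 30 mg BID by about 2 and the others by under 1. If 3.0 is raw or pooled over blinded arms, the loss may be fully offset. The loss rates, correlations and secondary effects used here are assumptions, so a net overstatement is not established.

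The consequence is slight either way. The clinical hypothesis names 60 mg QD or 60 mg BID, and both stay above 95% at 10% loss. The most sensitive dose is one the SAP itself describes as potentially sub-optimal. The documents set no numerical power target, and the table feeds into no test, estimate, alpha level or decision. A sentence on how the SD was obtained, what loss was expected and which secondary effects were simulated would be a courtesy to readers; the trial's conclusions do not depend on it.

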#### 5.2 Changes in the Conduct of the Study or Planned Analyses

#### 5.2.1 Changes in the Conduct of the Study

Not applicable.

#### 5.2.2 Changes to Analyses Prior to Database Lock

Not applicable.

#### 6. Data Handling and Analysis Conventions

#### 6.1 Study Treatment Conventions

#### 6.1.1 Analysis Days

Treatment day is defined as follows:

Table 6–1Analysis Day Definitions

Term	Description		
Treatment Day	Relative to treatment start date		
	If analysis date $\geq$ treatment start date:		
	• Day = analysis date – treatment start date + 1		
	$\circ$ Day 1 = treatment start date		
	If analysis date < treatment start date:		
	• Day = analysis date – treatment start date		
	$\circ$ Day -1 = day before treatment start date		
	$\circ$ There is no Day 0		

#### 6.1.2 Missing/Incomplete Treatment End Date

If the investigator is unable to provide the treatment end date, treatment end date will be imputed to the last available dosing record date.

#### 6.2 Analysis Visit Windows

#### 6.2.1 Efficacy

The analysis visit windows for efficacy endpoints based on daily eDiary data are defined as follows:

Table 6–2Efficacy Analysis Visit Definitions for eDiary Data

Analysis Phase	Analysis Visit (Derived)	eDiary Window
Pretreatment	Baseline	The first 28 days from screening visit
Treatment	Weeks 1–4	Treatment Day [1, 28]
	Weeks 5 – 8	Treatment Day [29, 56]
	Weeks 9 – 12	Treatment Day [57, 84]

## 6.2.2 Safety

The analysis visit windows for safety endpoints are defined as follows:

Analysis Phase	Analysis Visit (Derived)	Scheduled Study Visit (eCRF)	Window
Pretreatment	Baseline	Visit 2	Treatment Day $\leq 1$
		(Randomization)	
Treatment	Week 2	Visit 3	Treatment Day [2, 20]
	Week 4	Visit 4	Treatment Day [21,34]
	Week 6	Visit 5	Treatment Day [35, 48]
	Week 8	Visit 6	Treatment Day [49, 69]
	Week 12	Visit 7/ET	Treatment Day [70, the last double-blind visit]
	End of treatment		Last available assessment during double blind
			treatment period
	Week 16 (Safety	Visit 8	Treatment Day [the last double-blind visit +1, the
	follow-up)		last study visit]
	End of study		Last available assessment after treatment start date,
			i.e. occurs at final visit (expected Day 112) or ET

Table 6–3Safety Analysis Visit Definitions

Safety follow-up visit will be presented in analysis tables for clinical laboratory values and vital signs. End of Treatment is defined as the last available assessment during double-blind treatment period, i.e. on or before the treatment end date. End of Treatment results will be presented in analysis tables for clinical laboratory values and vital signs.

End of Study is defined as the last available assessment during the study, including double-blind and safety follow-up period. End of Study results will be presented in analysis tables for safety parameters, including but not limited to electrocardiograms, clinical laboratory values, and vital signs.

ET = early termination.

The following general conventions for repeated or unscheduled assessments will apply unless otherwise specified:

- The latest non-missing assessment within any analysis window will be flagged as the analysis value for any summaries by analysis visit
- All postbaseline assessments will be considered for PCS categorization
- All assessments will be included in respective listings

#### 6.3 Missing/Incomplete Date Conventions

Dates may be imputed with year, month, and day values under certain scenarios:

Complete Scenario Year Month Day Imputable Complete Yes Yes Yes 1 2 Yes Yes Yes 3 Yes Yes No¹ ____ 4 Yes Yes 5 Yes Yes No¹

Table 6–4Imputation Scenarios

	Complete			
Scenario	Year	Month	Day	Imputable
6	—	Yes	—	No ¹
7	—	—	Yes	No ¹
8	—			Yes

¹ Not allowed per database design.

Dates will be imputed initially toward a specified target date for imputable scenarios 2, 4, and 8, and adjusted against the latest reasonable dates. The initial imputed date is determined by the following algorithm:

#### Table 6–5Initial Imputed Date Algorithm

Available Year		Available Month (MM)		
(YYYY)	Missing	< Target Month	= Target Month	> Target Month
Missing	Target Date		—	
< Target Year	YYYY-12-31	YYYY-MM-LD		
= Target Year	Target Date	YYYY-MM-LD	Target Date	YYYY-MM-01
> Target Year	YYYY-01-01		YYYY-MM-01	

YYYY = available start date year; MM = available start date month; LD = last day of the month.

#### 6.3.1 Missing/Incomplete AE Start Date

AE start dates will be imputed as the minimum of the following:

- Initial imputed date, where target date = Treatment start date
- Complete end date

#### 6.3.2 Missing/Incomplete Medication Start Date

Medication start dates will be imputed as the minimum of the following:

- Initial imputed date, where target date = Treatment start date -1
- Complete end date

#### 6.3.3 Missing/Incomplete AE/Medication End Date

AE and medication end dates will be imputed as the minimum of the following:

- Initial imputed date, where target date = Treatment end date + 30
- Death date

#### 6.4 Efficacy Endpoint Conventions

#### 6.4.1 Derivation of Efficacy Endpoints Based on eDiary Data

*For analysis purposes, four weeks (28 days) will be considered as one month.* On a daily basis during the 4-week baseline period and throughout the double-blind treatment period, participants are to record eDiary information on the duration of headache, headache specific characteristics

and symptoms, the pain severity, and use of any acute headache pain medication. Daily headache diary data consists of data from "today's dairy" completed on that day and "yesterday's diary" completed on the following day. Participants are to report headache data in "today's diary" in the evening 19:00 to 23:59 and to complete "yesterday's diary" on the following day to add the remaining headache data of previous evening until midnight. In case participants miss "today's diary", they are able to report the whole-day headache data in "yesterday's diary" on the following day. In case participants miss "yesterday's diary", headache data from "today's diary" alone will be used as daily headache diary data. If both "today's diary" and "yesterday's dairy" are missing on one day, the daily headache diary data will be treated as missing.

Daily headache diary data will be merged from "today's diary" and "yesterday's diary" as following and will be used to derive MPM headache day and headache day.

- Daily headache total duration: summation of headache durations from "today's diary" and "yesterday's diary"
- Daily headache pain severity: the worst pain severity from "today's diary" and "yesterday's diary"
- Daily headache characteristics and symptoms: present if present in one of "today's diary" and "yesterday's diary"
- Daily acute headache medication usage: combination of acute headache medications usage from "today's diary" and "yesterday's diary"

For analysis purpose endpoint, the number of headache days during the first 28 days of the baseline phase, starting with the day of the screening visit, will serve as the "baseline", and change from baseline will be calculated for consecutive 28-day periods beginning with Day 1 (ie, Weeks 1-4, 5-8 and 9-12, corresponding to Days 1-28, 29-56 and 57-84). In order to be randomized, a participant should be in the baseline phase for at least 28 days and must report diary data for at least 20 days during the 28-day baseline period.

The 4-week *(monthly)* MPM headache days is defined as the total number of reported MPM headache days in the diary divided by the total number of days with diary records during each 4-week period and multiplied by 28. A minimum of 12 days' diary data during each *postbaseline* 4-week treatment period is required in order for the MPM headache migraine days to be evaluable for that particular period. If a subject does not have at least 12 days of diary data for any 4-week treatment period, the MPM headache days for that particular period will be considered as missing. MPM headache days will be derived for each participant at baseline and for each *postbaseline* 4-week treatment period (Weeks 1-4, 5-8, 9-12). The same method to derive MPM headache days will be used to derive headache days, *acute medication use days, and triptan use days*.

If a subject reports 'Yes' to the intake of allowed medication(s) to treat an acute migraine but does not list any of them in the diary, then the acute medication use days will not be counted in this situation.

